Allogeneic HB-adMSCs to provide immune support against COVID-19.

Each patient will be allocated a unique subject number at screening and will retain this number throughout the study. The first 4 patients (1 for each group) will receive their first infusions on weeks 0 and 2. Upon successful completion of infusion 2 for the first 4 patients, the DSMB will meet at least 48hrs after the last second infusion, to review safety. If permitted by DSMB, the rest of the patients can receive their infusions as long as all inclusion criteria have been met and none exclusion criteria is.

The Investigational Product is to be administered to eligible, enrolled patients by intravenous infusion at a dose that will depend on the group they have been randomized to:

- Group 1→2 x10⁸ cells at weeks 0, 2, 6, 10 and 14.
- Group 2→1 x10⁸ cells at weeks 0, 2, 6, 10 and 14.
- Group 3→5 x10⁷ cells at weeks 0, 2, 6, 10 and 14.
- Group 4→Placebo infusions at weeks 0, 2, 6, 10 and 14.

Every effort should be made to adhere to the dosing schedule. However, a scheduled infusion should not be administered if a patient has an ongoing AE that, in the Investigator's opinion, warrants holding the infusion.

Blinding

Blinding for Dose Administration

All patients, investigators, mixer, and site staff will be blinded to treatment assigned.

Amber bags covering the saline will be used for product infusion. Only subject ID, DOB and expiration date will be on the bag label, to ensure proper distribution. Mixer will inject product into the bag before handing off to the clinical team.

Blinding for Clinical Evaluators

To minimize assessment bias, clinical evaluators (data analysts and physicians) will be trained on how to maintain blinding to treatment as best as possible. "Best as possible" means that blinding will be maintained unless an adverse event occurs that requires unblinding the physician, which is determined by the medical monitor or DSMB. Training includes review of the process of blinding, describing who will be responsible for assigning product for the appropriate group, labels that will be used to identify subjects but not treatment group, and the process that should be followed if an adverse event occurs, triggering review by medical monitor and/or DSMB.

Planned Unblinding

Allogeneic HB-adMSCs to provide immune support against COVID-19.

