Unblinding of patient and researcher will occur in the case of adverse event suspected to be related to the investigational product, per the medical monitor and DSMB.

Regulatory authorities and/or the IRB may request the unblinding of data from one or more patients at any time.

Prior and concomitant conditions

The investigators should document all prior significant medical history. Additional conditions present at the time when informed consent is given and up to the time of first infusion (Week 0) are to be regarded as concomitant conditions. Illnesses first occurring or detected during the study and/or worsening of a concomitant condition during the study should be documented as AEs in the CRF.

Prior and concomitant medications

All medications, including over-the-counter treatments and preventative vaccines taken by the patient during the study, including those treatments initiated prior to the start of the study, must be recorded in the CRF. The entry must include the dose, regimen, route, indication, and dates of use.

Study Procedures

Table 2 outlines the timing of procedures, and assessments to be performed throughout the study.

Table 2. Schedule of Assessments

Visit Number	1	2	3	4	5	6	7	8	9
Weeks	N/A	Week 0	Week 2	Week 6	Week 10	Week 14	Week 18	Week 22	Week 26
Visit Name	Screening (Phone call)	Infusion-1 /Baseline	Infusion 2	Infusion 3	Infusion 4	Infusion 5	Follow Up	Follow Up	EOS
Window Period	Up to 45 days	±4 days	±4 days	±4 days	±4 days	±4 days	±4 days	±3 days	±3 days
STUDY PROCEDURES									
Informed Consent	X	X							
Inclusion and Exclusion Criteria	X	X							
Pre-infusion assessment		X	X	X	X	X			
Review of Medical History	X	X	X	X	X	X	X	X	X
Concomitant Medication Review	X	X	X	X	X	X	X	X	X

Allogeneic HB-adMSCs to provide immune support against COVID-19.

Vital Signs		X	X	X	X	X	X	X	X
Weight and Height ¹		X	X	X	X	X	X	X	X
Physical Examination		X	X	X	X	X	X	X	X
SF-36 Questionnaire		X	X	X	X	X	X	X	X
PHQ-9		X	X	X	X	X	X	X	X
Rapid antibody COVID-19		X							X
CBC with differential		X		X		X			X
Chemistry		X		X		X			X
Coagulation Panel		X		X		X			X
CRP		X		X		X			X
IL-6		X		X		X			X
IL-10		X		X		X			X
TNF alpha		X		X		X			X
HB-adMSCs Administration		X	X	X	X	X			
24-hour telephone encounter		X	X	X	X	X			
Adverse Event Monitoring		X	X	X	X	X	X	X	X
1. Height will only be measured at baseline									

Informed Consent (ICF)

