Prior to commencement of any trial related activity, the investigator or designated staff will obtain written informed consent from the patient.

Patient Re-Screening

If a patient is screened and fails to meet any study entry criteria may be re-screened only once. Such patient must be fully consented a second time before the second set of screening assessments take place and shall be assigned a new subject number. Investigator discretion should be exercised in determining who may be re-screened.

In case of doubt about the accuracy of screening laboratory value(s), the laboratory test(s) may be repeated provided that this can be done within the 45-day screening period without the need to repeat all other screening procedures (i.e., no re-screening).

If a patient is enrolled after they have been re-screened, such subject shall be assigned a new subject ID number, different from the previous attempt to enroll.

Assessments by Week

Allogeneic HB-adMSCs to provide immune support against COVID-19.

Assessments will occur as outlined in the following subsections. For visits at Weeks 0 through 26, there will be a window of ± 4 days.

Screening

The Screening visit will last up to 45 days. These are the procedures to be performed during this visit:

- Demographic Information will be obtained.
- Medical History and Current conditions will be obtained,
- Concomitant Medications will be obtained. Every medication listed should match a condition in the medical history.
- Ascertain patient eligibility by evaluating patient results against the inclusion/exclusion criteria.

Upon completion of all Screening procedures, the Principal Investigator must confirm and document the patient eligibility in the “Screening Result” CRF and notify the Sponsor via Fax or e-mail.

Infusion Visits (Baseline/Week 0, Week 2, Week 6, Week 10, and Week 14)

Generally, these are the procedures to be performed at every infusion visit. For details, please refer to the schedule of assessments.

Baseline assessments will be taken before the administration of the first infusion. A second assessment of informed consent shall be obtained prior to the first infusion.

- Pre-infusion assessment will be made by telephone call in the morning prior to all infusion visits to assess any occurrence of symptoms. In the event a subject is exhibiting symptoms, the subject will be asked to remain home. ● Weight will be measured
- Vital Signs will be measured.

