- Concomitant medications will be reviewed and updated if necessary.
- Medical History will be reviewed and updated if necessary. If the patient reported a medication which does not match the current medical history, further investigation will be required to determine whether it was an Adverse Event, or the patient just forgot to mention it before. If it is found to be an AE, it should be recorded in the appropriate CRF. If the patient forgot to mention it before, a note to file (NTF) should be made to clarify the case.
- Blood samples will be collected for laboratory assessments at weeks 0, 2, 6, 10, 14, and 26.

Allogeneic HB-adMSCs to provide immune support against COVID-19.

- Pre-infusion medications: Prior to IP administration the subject will be administered: Aspirin 81 mg per mouth, and Loratadine 10 mg per mouth
- Physical examination performed by principal investigator or sub-investigator.
- Patient will complete SF-36 and PHQ-9 assessments.
- Administer investigational product.
- Monitor for AEs. Observe the patient for at least 1 hour after infusion for symptoms of infusion-related reactions and allergic reactions, including anaphylaxis (See Appendix 1).
- Instruct the patient on recognition of delayed serious allergic reactions, including anaphylaxis and seeking for medical assistance.
- Telephone encounter 24 hours after the infusion will be performed to assess the occurrence of AEs.

Follow Up Weeks 18, and 22.

- Weight will be measured
- Vital Signs will be measured.
- Concomitant medications will be reviewed and updated if necessary.
- Medical History will be reviewed and updated if necessary. If the patient reported a medication which does not match the current medical history, further investigation will be required to determine whether it was an Adverse Event, or the patient just forgot to mention it before. If it is found to be an AE, it should be recorded in the appropriate CRF. If the patient forgot to mention it before, a note to file (NTF) should be made to clarify the case.
- Physical examination performed by principal investigator or sub-investigator.
- Patient will complete SF-36 and PHQ-9 assessments.
- Instruct the patient on recognition of delayed serious allergic reactions, including anaphylaxis and seeking for medical assistance.
- Telephone encounter 24 hours after the infusion will be performed to assess the occurrence of AEs.

Weeks 26 (End of the Study or Early Discontinuation Visit)

- Weight will be measured

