The PHQ-9 is the depression module, which scores each of the nine DSM-IV criteria as "0" (not at all) to "3" (nearly every day). It is not a screening tool for depression, but it is used to monitor

Allogeneic HB-adMSCs to provide immune support against COVID-19.

the severity of depression. In addition to making criteria-based diagnoses of depressive disorders, the PHQ-9 is also a reliable and valid measure of depression severity.

TNF- α

The primary role of TNF is in the regulation of immune cells. TNF, being an endogenous pyrogen, is able to induce fever, apoptotic cell death, cachexia, inflammation and to inhibit tumorigenesis and viral replication and respond to sepsis via IL1- & IL6-producing cells.

IL-10

IL-10 is a cytokine with multiple effects in immunoregulation and inflammation. It downregulates the expression of Th1 cytokines, MHC class II antigens, and co-stimulatory molecules on macrophages. It also enhances B cell survival, proliferation, and antibody production.

IL-6

Interleukin 6 (IL-6) is an interleukin that acts as both a pro-inflammatory cytokine and an antiinflammatory myokine. In humans, it is encoded by the *IL6* gene.

Safety Assessments

Safety assessments (vital signs, weight, physical examinations, AEs, routine clinical laboratory tests (CBC, CMP, PT and PTT/INR) will be performed at the visits specified in the schedule of assessments in Table 2.

Vital Signs, Height, and Weight

Vital signs (body temperature, pulse, oxygen saturation, systolic and diastolic blood pressure measurements) will be evaluated at the visits indicated in the schedule of assessments. It is important that all vital signs be measured after the patient has been resting in a sitting position for at least 5 minutes. Blood pressure measurements are to be taken in the same arm for the duration of the study. Body weight (without coats and shoes) will be recorded whenever vital signs are recorded, and height (without shoes) will be recorded at Infusion 1 (baseline) only.

Vital sign measurements will be repeated if clinically significant or machine/equipment errors occur. Out-of-range blood pressure and pulse measurements will be repeated at the Investigator's discretion. Any confirmed, clinically significant vital sign measurements will be recorded as AEs and followed up as such.

Physical Examination

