It is the responsibility of the Principal Investigator to oversee the safety of the study at his/her site. This safety monitoring will include careful assessment and appropriate reporting of adverse events as noted above. At Hope Biosciences, [name], MD [contact] will be responsible for reviewing any reported AEs and SAEs to determine if changes to the study need to be made or if the study should be stopped for the protection of patients. DSMB will review all deaths (to assure non-attribution), cases of anaphylaxis or suspected anaphylaxis, thromboembolic events, new malignancy/tumor, infections/hospitalizations (including unrelated to COVID-19 but due to underlying condition). After 15 subjects diagnosed with COVID-19, 5 subjects are hospitalized, or 3 subjects in the ICU, DSMB will review. DSMB will also review safety data at mid-point of the study.

Risks

Potential Risks of the Investigational Product and Clinical Investigation

Risks Associated with HB-adMSCs

Respiratory Risks:

A potential risk is that the infusion could initiate a VTE event with subsequent cardiopulmonary sequelae of respiratory failure and/or right heart strain/failure. We plan to monitor oxygen saturation, and respiratory rate/work of breathing for the first 2 hours post- infusion. The patient will be examined for VTE events (clinical exam, oxygen saturation) during each infusion visit and at each follow-up visit.

Hepatic Risks:

The reticuloendothelial system can sequester immature blood elements, theoretically resulting in hepatic injury. An acute elevation of the AST/ALT hepatic enzymes > 900 U/dl post-infusions will be considered an infusion related adverse event. This level is based upon the organ system scoring definitions for moderate hepatic failure and corresponds to the CTCAE v4.03 Grade 4 adverse event. It is unlikely that "end vessel" micro-thrombosis would occur in the liver due to the dual blood supply of the liver and the lung is the first pass organ. A CMP will be obtained at follow-up visits.

Coagulation Cascade:

A coagulation panel will be obtained at screening, baseline, infusion and the follow-up visits. The patient will be monitored for the development of venous thromboembolic events (see pulmonary monitoring above) as well as for the development of clinical deep vein thrombosis (limb swelling, tenderness, discoloration).

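### Safety-laboratory schedules conflict, and the DSMB review that releases the remaining patients requires no post-treatment laboratory result

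*Protocol*

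**What the plan says.** **The review.** In the Staggering section, one patient per group is infused at Weeks 0 and 2. Then: "Upon successful completion of infusion 2 for the first 4 patients, the DSMB will meet at least 48hrs after the last second infusion". If the board permits, the remaining eligible patients may be dosed. The section does not list the data the board must have.

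**The laboratory schedule.** Four parts of the protocol bear on it.

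- Table 2, in the row "CBC with differential" and in the chemistry and coagulation rows, marks Weeks 0, 6, 14 and 26. The Week 2 and Week 10 columns are empty.
- Safety Assessments ties the tests to that table: "routine clinical laboratory tests (CBC, CMP, PT and PTT/INR) will be performed at the visits specified in the schedule of assessments in Table 2".
- Infusion Visits also points to the table ("For details, please refer to the schedule of assessments") and says "Baseline assessments will be taken before the administration of the first infusion", so the Week 0 sample is not a post-treatment sample. Its own procedure list then says: "Blood samples will be collected for laboratory assessments at weeks 0, 2, 6, 10, 14, and 26". It does not name the tests.
- The Risks section says, under Coagulation Cascade, "A coagulation panel will be obtained at screening, baseline, infusion and the follow-up visits" and, under Hepatic Risks, "A CMP will be obtained at follow-up visits".

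**Events that need a blood test.** Hepatic Risks counts an acute AST/ALT rise above 900 U/dl after infusion as an infusion-related event and equates it with CTCAE Grade 4. The fifth Study Stopping Rule covers Grade 4-5 events judged to be linked in time to the infusion.

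**The concern.** A sentinel stage is there to find problems before wider exposure. If the site follows Table 2 and the board meets at the first permitted date, the review of the last-dosed sentinel rests on vital signs, examination, reported adverse events and the 24-hour telephone call. None of these would show a hepatic, renal or coagulation change without symptoms. One such change, the AST/ALT rise, falls within the trial's own stopping rules if judged linked in time to the infusion. The board can ask for more data, but it cannot recover a sample that was not drawn at the time.

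The conflict between schedules matters in its own right. Two people reading different pages would draw blood from the sentinels on different dates, and neither would be plainly wrong.

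**Working it through.** **Inputs.** Total 53 (Randomization; capped at 53 in Determination of Sample Size). Sentinels 4, of whom 3 receive cells (Staggering). Infusions at Weeks 0 and 2. Review at least 48 hours after the last second infusion. Visit window ±4 days through Week 14 (Table 2). The figure of 53 rests on banked patients, not on a power calculation, so there is no calculation to reproduce.

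**Patients released.** 53 − 4 = 49, and 49/53 = 92%. This is an upper limit because 53 is a cap.

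**The schedules side by side.**

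| Source | Timepoints | Added to Table 2 |
|---|---|---|
| Table 2 (CBC, chemistry, coagulation) | Weeks 0, 6, 14, 26 | none |
| Infusion Visits list (tests not named) | Weeks 0, 2, 6, 10, 14, 26 | Weeks 2, 10 |
| Coagulation Cascade (coagulation only) | Screening, Weeks 0, 2, 6, 10, 14, 18, 22, 26 | Screening, Weeks 2, 10, 18, 22 |
| Hepatic Risks (CMP) | Follow-up visits | Weeks 18, 22 |

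**Timing if Table 2 is followed.** Day 0 is the first infusion of the last-dosed sentinel.

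- Infusion 2: day 14 (10 to 18 with the window).
- Earliest meeting: 14 + 2 = day 16 (12 to 20).
- First post-treatment draw, Week 6: day 42 (38 to 46).
- Gap: 42 − 16 = 26 days. Shortest 38 − 20 = 18; longest 46 − 12 = 34.

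No use of the windows closes the gap for this patient. Another sentinel could have a Week 6 sample by then only if first dosed about 26 days (18 to 34) before the last one.

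**Timing if the Infusion Visits list is followed.** Each sentinel has a Week 2 sample. The list places blood sampling ahead of product administration, so the sample most naturally reflects infusion 1 alone. No text clearly schedules a draw after infusion 2 and before day 16. The Coagulation Cascade statement would also give a Week 2 coagulation panel, but that does not measure AST/ALT.

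**How much a laboratory check could show.** The chance of at least one event in 3 treated patients is 1 − (1 − p)³. The documents give no event rate, so p is assumed.

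| Assumed p | Chance of seeing an event |
|---|---|
| 1% | 1 − 0.99³ = 3% |
| 5% | 1 − 0.95³ = 14% |
| 10% | 1 − 0.90³ = 27% |
| 20% | 1 − 0.80³ = 49% |

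With 0 events in 3, the one-sided 95% upper limit is 1 − 0.05^(1/3) = 63%.

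**The case against.** The strongest reply is that the gap is not certain. The Infusion Visits list gives every sentinel a Week 2 sample, and the Risks section gives a coagulation panel at infusion visits. The 48 hours is a minimum, release needs the board's permission, and Unscheduled Visits allows extra assessments. The Synopsis counts clinical laboratory values among the safety criteria and names the DSMB among those monitoring safety, so laboratory data lie within the remit of a safety review. The protocol presents hepatic injury as a theoretical risk and reports earlier use of the product as well tolerated. With three treated patients, a clean panel rules out little.

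Much of this stands. A reader might infer that the board will release 49 patients with no laboratory data at all. The documents do not support that: it requires Table 2 to prevail, a meeting at the earliest date, no request for tests and no earlier-dosed sentinel with a Week 6 result. Nor do they support the inference that 49 patients would be infused before those results arrive, because no enrolment rate is given.

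What the reply does not remove is the conflict itself, and the fact that no result is tied to the review under either schedule. A general remit to review laboratory data does not create a sample. Two sections defer to Table 2, so a site following it would be acting reasonably. The other controls also vary by section: Instructions for Administration asks for at least 2 hours of observation after infusion, while Investigational Plan and Infusion Visits ask for 1 hour.

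**Conclusion.** The protocol contradicts itself on safety-laboratory timing, and the contradiction falls on the sentinel review. Under Table 2, the last-dosed sentinel has no scheduled post-treatment result when up to 49 of 53 patients may first be released; the gap is 26 days (18 to 34). Under the Infusion Visits list, a Week 2 sample after infusion 1 exists, but its result is not required and no draw clearly follows infusion 2 before the earliest meeting.

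This assumes a meeting at the first permitted date and no additional tests. The documents do not settle which schedule governs. They also do not say whether the sentinel stage is already over; if it is, only the reconciliation of schedules still helps.

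The gain is modest, given a 63% upper limit after 0 events in 3. This is a cheap improvement to one safety review, not a finding that the trial is unsafe.

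**What to change.** 1. **Tie the review to results.** Add a Week 2 draw of CBC, chemistry and coagulation to Table 2, before infusion 2, at least for the four sentinels. State in Staggering that the DSMB meets no earlier than 48 hours after the last second infusion, and only with those results in hand for all four. Cost: 4 × 1 = 4 samples if the site now follows Table 2. There is no extra draw if it follows the Infusion Visits list, provided that draw covers all three panels. The Week 2 visit already exists.
2. **Preferably, add one routine sample after infusion 2 and before the meeting** in the same four patients, because the AST/ALT event is defined as acute. Cost: up to 4 more samples, so at most 8 in all. A short extra visit may be needed, since Table 2 has no site visit between Weeks 2 and 6 and the 24-hour contact is by telephone. There is also some wait for results; the documents give no turnaround time.
3. **Reconcile Table 2 with Infusion Visits, Safety Assessments and Risks.** Do not delete the hepatic and coagulation tests in the Risks section merely to match Table 2, because the protocol offers them against named risks. Any test that is dropped should be dropped for a stated safety reason. For a site now following Table 2, adding Weeks 2 and 10 for everyone costs up to 53 × 2 = 106 patient-draws. Adding Weeks 18 and 22 as well brings this to 53 × 4 = 212, before any screening sample. All four are existing visits. The sentinel review itself needs no added draws in the other 49 patients. The screening coagulation panel needs a decision, since Table 2 lists screening as a telephone call.

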Allogeneic HB-adMSCs to provide immune support against COVID-19.

Details of the investigational product

Allogeneic HB-adMSCs is to be administered as an IV infusion with a syringe containing 5×10^7 cells. Each syringe will be provided by Hope Biosciences on the day of the infusion after all quality control assays have been performed and the results are within normal range.

Instructions for Administration

The designated study staff will administer the investigational product in the following manner:

- Prior to administration, visually inspect the infusion solution for particulates. If foreign particles are present, do not use the solution.
- Emergency equipment, such as epinephrine, antihistamines, and corticosteroids must be available in the event of infusion-related reactions.
- Start IV administration after dilution.
- Administer the infusion solution over a period of 1h. Observe the patient for at least 2 hours post-infusion for acute infusion-related reactions, including anaphylaxis. See Appendix 1 for guidelines on diagnosing anaphylaxis.
- Do not store or reuse any unused portion of the infusion solution. Any unused product or waste material should be disposed.
- Volume of study drug infused, start times, and stop times will be recorded. If any portion of the infusion (cell solution) is discarded, the reason will be recorded in the CRF.
- The patient will be monitored for a total of 3 hours from drug exposure to discharge.
 - a. During the Investigational product administration (1 hour) vital signs will be measured at minute 0, 15, 30 and 45.
 - b. Post infusion, vital signs will be measured at minute 0, 30 and 60.

Investigational Product Assignment and Infusion Schedule (Randomization and Staggering)

Randomization

A total of 53 eligible subjects will be randomized to either placebo or treatment group within the associated study arm at baseline. Randomization will determine whether the subject receives placebo or HB-adMSCs.

A neutral, third-party personnel will be responsible for assigning the participants' treatment group. This role will be referred to as 'randomizer'. The designated personnel from the drug manufacturer will be responsible in labeling and packaging the investigational product for each participant. This role will be referred to as 'mixer'. Participants' names are not disclosed to the mixer and the unblinded information will only be known to the randomizer.

Staggering

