2.2. Study Design

Overview of Study Design and Key Features	
Randomized, double-blind, placebo-controlled, parallel group study	
Design Features	
 • Randomized, double-blind, Placebo controlled, parallel group study. • 53 Subjects • 4 Treatment groups 
 ▪ Group 1 → 2 x10⁸ cells (allogeneic HB-adMSCs 200MM) ▪ Group 2 → 1 x10⁸ cells (allogeneic HB-adMSCs 100MM) ▪ Group 3 → 5 x10⁷ cells (allogeneic HB-adMSCs 50MM) ▪ Group 4 → Placebo • Duration of treatment: up to 26 weeks, and overall study includes screening (up to 45 Days prior to randomisation), and 5 treatment visits after randomisation includes Infusion 1 (Week 0), Infusion 2 (Week 2), Infusion 3 (Week 6), Infusion 4 (Week 10) and Infusion 5 (Week 14). And follow up weeks of 18, 22 and end of study at Week 26.
Dosing	
 • Allogeneic HB-adMSCs is to be administered as an IV infusion. Each 10-mL syringe contains 5 x 10⁷ cells suspended in 5 mL of sterile saline to be diluted in 250 mL sterile saline.
Treatment Assignment	
 • Participants will be randomised 3:1 to receive HB-adMSCs treatments or Placebo.

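### The protocol calls the mixer blinded, but the mixer's tasks reveal the arm; no matching of bag volume across arms is described

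*Protocol*

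**What the plan says.** The protocol's section Blinding for Dose Administration states: "All patients, investigators, mixer, and site staff will be blinded to treatment assigned". The Randomization section adds: "Participants' names are not disclosed to the mixer and the unblinded information will only be known to the randomizer".

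The same two sections give the mixer two tasks. Randomization says: "The designated personnel from the drug manufacturer will be responsible in labeling and packaging the investigational product for each participant". That person is the mixer. Blinding for Dose Administration says: "Mixer will inject product into the bag before handing off to the clinical team". The bag label carries the subject ID, date of birth and expiration date.

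The protocol describes one presentation, a syringe of 5 x 10^7 cells, and gives no syringe volume. The SAP, section 2.2 (Dosing), gives the volume: "Each 10-mL syringe contains 5 x 10⁷ cells suspended in 5 mL of sterile saline to be diluted in 250 mL sterile saline". The per-infusion doses are 2 x 10^8, 1 x 10^8 and 5 x 10^7 cells. The synopsis describes placebo as vehicle without cells and gives neither a volume nor a number of syringes.

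Under Instructions for Administration, in a list of steps assigned to the designated study staff, the protocol says: "Volume of study drug infused, start times, and stop times will be recorded".

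The masking measures described are amber covers over the bags, labels that identify the subject but not the treatment group, withholding names from the mixer, and training of data analysts and physicians in keeping the blind.

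**The concern.** There are two separate issues, and they differ in strength.

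The first is a contradiction within the protocol. A person who prepares a subject-specific bag, with a dose that differs by arm, is classed as blinded. Withholding names conceals who the participant is, not which arm the subject ID is in. The label matters because a role recorded as blinded needs no separation from anyone, and none is stated for the mixer. The mixer belongs to the manufacturer, which the protocol also names as sponsor, and the Interim Analysis section lets the sponsor look at efficacy data at any time.

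The second is an inference. If the arms need different numbers of syringes and nothing equalises the added volume, the volume written down at each of five infusions could point to the arm. An amber cover does not affect a recorded volume.

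One primary endpoint is the incidence of fever, cough or breathing difficulty. Symptoms are asked about by telephone before each infusion, and adverse event causality rests on medical judgement. Knowledge of the arm could influence each of these.

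**Working it through.** The plan states no figure on this point, so there is none to reproduce. The check is a comparison of passages plus simple arithmetic.

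**Step 1: the mixer's role.**
- Stated status: blinded, with allocation known only to the randomizer (protocol, Blinding for Dose Administration and Randomization).
- Stated tasks: label and package product per participant, then inject it into the bag (same sections).
- Syringes per infusion = dose / (5 x 10^7 cells per syringe):
  - 200MM: 2 x 10^8 / 5 x 10^7 = 4
  - 100MM: 1 x 10^8 / 5 x 10^7 = 2
  - 50MM: 5 x 10^7 / 5 x 10^7 = 1
  - Placebo: no cells; presentation not described

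To package the right product for a subject ID, the mixer must be told or must see which of these applies. Hiding the arm would need something like dummy or pre-masked syringes prepared by someone else. Neither document describes that. This step uses no volume figure.

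**Step 2: bag volumes.** Inputs are 5 mL per syringe and 250 mL of saline (SAP 2.2). Added volume = 5 mL x syringes; total = 250 mL + added volume.

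| Arm | Syringes | Added (mL) | Total (mL) | Over 250 mL |
|---|---|---|---|---|
| 200MM | 4 | 20 | 270 | 20/250 = 8% |
| 100MM | 2 | 10 | 260 | 10/250 = 4% |
| 50MM | 1 | 5 | 255 | 5/250 = 2% |
| Placebo | not given | assumed 0 to 20 | 250 to 270 | 0% to 8% |

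**Step 3: spread across all four arms,** (largest - smallest) / smallest:
- Placebo adds 0 mL: (270 - 250) / 250 = 8.0%.
- Placebo adds 5 to 20 mL: the smallest bag is 255 mL, so (270 - 255) / 255 = 5.9%.
- Placebo between 0 and 5 mL: between these two values.

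Any single placebo volume can match at most one active arm, because the active arms differ among themselves (5, 10 and 20 mL).

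**Step 4: what is recorded.** The recorded item could mean the whole bag or only the cell suspension. On the first reading the active arms run from 255 to 270 mL. On the second they run from 5 to 20 mL, a ratio of 20 / 5 = 4. The record differs by arm on either reading.

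**The case against.** The strongest reply is that only the mixer's label is shown to be wrong. A reader might infer that the trial's blind as a whole has failed. The documents do not support that: an unblinded preparer does not by itself unblind participants, investigators or evaluators. Evaluators are to be trained in keeping the blind, and names are kept from the mixer. This stands. It does not rescue the claim that the mixer is blinded.

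On volume, the reply also has force:
- No sentence says the bag volumes differ. The 5 mL and 250 mL figures come from one dosing line in the SAP, which describes a single syringe and not how the larger doses are made up. A preparation manual not shown here could specify matching. What the documents support is that matching is not described.
- An 8% spread might be taken as the size of the leak. It holds only if placebo adds nothing, which is not stated.
- The sentence on recording volume is passive. Its link to blinded staff comes from the heading of the list it sits in, read together with the statement that site staff are blinded. Nothing says that those who assess symptoms or causality see the record, or know which volume goes with which arm.
- On bag totals, 50MM and a placebo with nothing added would differ by 5 mL in 250 mL, which could easily go unnoticed.

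All four limits are accepted. They make the volume issue a gap to close, not a finding that the arm was revealed.

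**Conclusion.** The statement that the mixer is blinded, and that only the randomizer knows the allocation, is wrong as written. It conflicts with the mixer's own tasks and with doses that imply 4, 2 or 1 syringes or cell-free vehicle. The conclusion rests on the single syringe presentation described and on the absence of any masked preparation step in either document.

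The volume issue is a reasonable inference of lesser certainty. The documents' figures imply 255, 260 and 270 mL for the active arms. Over an assumed placebo addition of 0 to 20 mL, the spread across arms is about 6% to 8%. It is a possible route to unblinding the staff who record or see the volume. The documents do not show that anyone was unblinded by it, and preparation instructions not seen here may already deal with it.

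The point should be corrected, since the affected assessments include a symptom endpoint and causality judgements. It does not establish that the results are biased.

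**What to change.** 1. Reconcile the Randomization and Blinding for Dose Administration sections. Name the mixer as unblinded alongside the randomizer. State that the mixer has no contact with participants, evaluators or data analysts and does not share allocation until database lock.
2. State that every bag, including placebo, is brought to the same added volume with the cell-free vehicle already used for placebo, leaving the cell doses unchanged. As an illustration, matching to the largest implied addition of 20 mL would need 20 - 20 = 0 mL of vehicle for 200MM, 20 - 10 = 10 mL for 100MM, 20 - 5 = 15 mL for 50MM and 20 - 0 = 20 mL for placebo. If a preparation manual already does this, cite it.
3. Keep recording the volume infused. Once volumes match, a complete infusion no longer points to the arm, and the record is needed to describe partial infusions. If volumes cannot be matched, restrict access to that record until database lock.

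The cost is a small extra preparation step and the separation of one existing role. If infusions are already complete, step 2 can no longer be applied. The sponsor can still correct the blinding statement, document who knew allocations, restrict the volume record until lock and report the limitation.
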